CPRD Internal Validation. 100 random sets of notes of patients aged 16-35 years with first time T ASD will be identified in CPRD. First time T ASD will be those patients with at least two years of data (washout period) before a first time entry read code for shoulder dislocation and with at least a further two years of follow up coding. These notes will be assessed for: use of shoulder dislocation codes for traumatic dislocation; confirming first time shoulder dislocation; confirming traumatic cause; and assessing the subsequent codes used for further events. Physiotherapy referral codes regards physiotherapy will also be assessed especially in terms of data on frequency of therapy, place of therapy (hospital or community) or type of therapy. Overall, data quality and completeness will be assessed using the GP questionnaire service (Appendix I) provided by CPRD. This questionnaire is based on the validation algorithm in Appendix H. Those risk factors that may play an important role as predictors of further re-dislocation and that are identifiable in CPRD will also be recorded. This analysis would ascertain which factors are reliably identifiable in CPRD and inform any formal analysis in WP2 regards future predictors.

Prevalence Rates (External Validation). We will compare age-gender prevalence rates of first time dislocators identified in our study with those of similar studies in other settings [7, 20]. This will externally validate GP and primary care coding of this condition. This external validation study will itself provide first time age and gender prevalence data on traumatic anterior shoulder instability in the UK.

During work package 1, if the analysis of the notes indicates that first time dislocation coding and recurrent dislocation coding is poor then the study cannot proceed and will be STOPPED (Red Light). To quantify this if during our review of coding and free text entries on patients with first time T ASD, if the positive predictive value of CPRD codes is $\geq 75\%$ (% recorded according to READ/OXMIS codes that are confirmed in the free text search) then we will continue to Stage 2 (Green Light). We would also take this opportunity to estimate the sensitivity of T ASD coding by using the algorithm on CPRD codes of alternative coding diagnose to include, but not limited to, shoulder pain, rotator cuff disorder, shoulder OA.

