Appendix I

GP CPRD Validation Questionnaire for the UK.TASH-D Study

Dear Colleague,

Thank you for completing this questionnaire as a practice connected to the CPRD database. The UK.TASH-D study will use the CPRD to investigate the treatment of first time traumatic anterior shoulder dislocation. As you know, shoulder dislocations often recur and we are investigating whether surgery makes recurrence less likely after a first episode. We will be completely reliant in the main phase of this study on electronic codes to identify recurrences.

Before starting the main phase, we need to know whether we can reliably identify ‘New dislocation episodes’ or whether these tend to be recorded as a ‘Review’ of the same problem (without a further dislocation occurring). Conversely, we need to know if codes apparently indicating a ‘further’ dislocation episode are in fact a ‘Review’ of the problem. We also need to confirm that codes recorded in primary care as ‘dislocation’ actually reflect this diagnosis, rather than less specific conditions affecting the shoulder.

We are therefore looking at a national sample of records that indicate a shoulder dislocation, and by completing the following questionnaire on your patient, you will help tell us:

- 1) Was this actually a traumatic shoulder dislocation?
- 2) Did further episodes occur over the following two years, and if so, how many true recurrences were recorded as ‘New’ episodes?
- 3) Were there any examples of ‘New’ recurrences being recorded as a ‘Review’ of the original problem?

If the coding proves valid and reliable, then a CPRD dataset will be linked to a Hospital Episode Statistics (HES) dataset to compare surgical versus conservative treatment (including physiotherapy) on recurrent dislocation rates. Our aim is that this will result in national pathway guidelines for the management of this condition in primary care.

Thank you in anticipation of your help

The UK.TASH-D study team.

Number	Question	Response (please tick)	
		Yes	No
1.	Is shoulder dislocation, an unstable shoulder, or shoulder instability caused by INJURY documented in the patient’s notes?	(If YES go to Q5)	(If NO go to Q2)
2.	Is shoulder trauma or shoulder injury documented in the patient’s notes?	(If YES go to Q3)	(If NO go to Q3)

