3.	Do MRI or X-ray imaging reports confirm a diagnosis of traumatic dislocation by mentioning the presence of Hill Sachs, Bankart lesion, labral tear, labral detachment, dislocation, relocation, bony Bankart?	(If YES go to Q5)	(If NO go to Q4)

This project was funded by the National Institute for Health Research Health Technology Assessment (project number 14/160/01).

The views and opinions expressed therein are those of the authors and do not necessarily reflect those of the HTA, NIHR, NHS or the Department of Health.

4.	Do Hospital letters from specialists or physiotherapists confirm traumatic instability or traumatic shoulder dislocation?	(If YES go to Q5)	(If NO go to Q8)
5.	Is there any record of a dislocation prior to the CPRD first registration date at your practice?	(If YES go to Q6)	(If NO go to Q6)
6.	Are there any further dislocation codes in the record during the 2 years after the first dislocation code?	(If YES go to Q6b)	(If NO go to Q6c)
6b.	If YES is it clear (for each one) that this is a further dislocation episode rather than simply a review of the problem?	(If YES go to Q7)	(If NO go to Q7)
6c.	If NO, have there been any further dislocations recorded during the following 2 years that are not electronically coded?	(If YES go to Q7)	(If NO go to Q7)
7.	Are there any physiotherapy treatment codes for 2 years after the first dislocation code?	(If YES go to Q7b)	(If NO go to Q7c)
7b.	If YES is it clear that this physio code indicates the patient received physiotherapy for their shoulder?	(If YES go to Q8)	(If NO go to Q8)
7c.	If NO, is there any documentation that the patient has received physiotherapy for their shoulder without a code being entered?	(If YES go to Q8)	(If NO go to Q8)
8.	If your specific responses to this questionnaire indicate that this patient has not had a traumatic shoulder dislocation but your reading of the notes or your knowledge of the patient suggest they might have please tick the YES box, otherwise tick the NO box.	The end – thank you	The end – thank you

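### The stop-go rule before WP2 sets no separate accuracy threshold for recurrence codes, which are the primary outcome, and the GP form measures their accuracy only coarsely

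*Protocol*

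**What the plan says.** Section F (CPRD Internal Validation) gives a stop rule in words and a go rule in numbers. In words, the project ends if "first time dislocation coding and recurrent dislocation coding is poor then the study cannot proceed and will be STOPPED (Red Light"). The next sentence offers to quantify this and sets one threshold: in a review of coding and free text "on patients with first time T ASD, if the positive predictive value of CPRD codes is" at least 75%, WP2 goes ahead. The PPV is the percentage "recorded according to READ/OXMIS codes that are confirmed in the free text search". Neither sentence says whether index codes, recurrence codes or both are counted. The same section lists, among the things WP1 will look at, "and assessing the subsequent codes used for further events".

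The primary outcome in Section L is time to re-dislocation within two years. The covering letter in Appendix I tells GPs: "We will be completely reliant in the main phase of this study on electronic codes to identify recurrences". It also says the form will show "how many true recurrences were recorded as" new episodes. Three questions bear on this, each with a yes/no tick:

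- Q6 asks whether any further dislocation code exists in the two years.
- Q6b goes to those with Q6 = yes: "If YES is it clear (for each one) that this is a further dislocation episode rather than simply a review of the problem"?
- Q6c goes only to those with Q6 = no: "have there been any further dislocations recorded during the following 2 years that are not electronically coded"?

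**The concern.** WP1 exists to show that the codes can carry the main study. The code that matters most is the one defining the event, because a follow-up visit entered as a fresh dislocation would look like an outcome. Section F recognises this in words but puts no number on it. A decision made on the stated number could therefore be favourable while the outcome code is unreliable. Read literally, the word joining the two kinds of coding also requires both to be poor before the study stops.

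False recurrence codes spread evenly over the two groups pull the hazard ratio towards 1 and cost power. They can also affect exposure: Sections F and J require no further dislocation code before surgery, so a review visit coded as a dislocation would remove a genuine early-surgery patient.

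**Working it through.** **1. The planned size.** Section G: 25% versus 20% at two years, two-sided 5%, 90% power, 10% loss, equal groups.

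- Hazard ratio = ln(0.80)/ln(0.75) = 0.776, stated as 0.78.
- Events: 652 (Schoenfeld) or 659 (Freedman), against 656 stated.
- With exponential loss of 10% over two years, the mean event probability is 0.2140, and 656/0.2140 = 3,065. The plan's figure is reproduced and is not in dispute.

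**2. What the 75% rule lets through.**

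- *Index codes only.* Recurrence codes do not enter, so the chance of passing does not depend on their accuracy.
- *Both kinds pooled.* Take 80 index codes (100 forms at the 80% return rate quoted by CPRD; that 100 are sent is an assumption) and 20 recurrence codes (25% of 80, one each; also an assumption). Passing needs 0.75 × 100 = 75 confirmed.

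| Index PPV | Index codes confirmed | Recurrence codes needed | Recurrence PPV that still passes |
|---|---|---|---|
| 80% | 64 | 11 of 20 | 55% |
| 85% | 68 | 7 of 20 | 35% |
| 90% | 72 | 3 of 20 | 15% |

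With 32 recurrence codes instead (40% of 80), passing needs 0.75 × 112 = 84. An index PPV of 90% then passes with 12/32 = 37.5%.

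**3. What the form can estimate.**

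- Q6b among Q6 = yes gives a patient-level PPV.
- Q6c among Q6 = no gives a patient-level negative predictive value.
- Q6b is one tick for all later codes, so the promised count cannot be formed, and a patient with one true and one review code has no informative answer.
- A No to Q6b mixes a known review with an unclear record.
- Q6c is skipped for anyone with a later code.
- No question asks which shoulder was involved, and the Appendix D descriptions carry no side.

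**4. Precision (exact 95% intervals at an observed PPV of 75%).** With 20% to 25% of 80 patients carrying a later code, 12/16 gives 48% to 93% and 15/20 gives 51% to 91%. If false codes raised the share to 30%, 18/24 gives 53% to 90%.

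**5. Effect on the main analysis.** Assume true risks of 25% and 20% and the same false-positive probability f in both groups among patients with no true event. Choose f so that true events divided by coded events equals the PPV. The mean true risk is 0.225. Events = 3,065 × 0.95 × mean coded risk; power = Φ(√events × |ln HR|/2 − 1.96).

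- No false codes: 655 events, HR 0.776, power 90%.
- PPV 75%: mean coded risk 0.225/0.75 = 0.300; f = 0.075/0.775 = 0.097. Coded risks are 0.25 + 0.097 × 0.75 = 32.3% and 0.20 + 0.097 × 0.80 = 27.7%. HR = ln(0.723)/ln(0.677) = 0.83; 873 events; power 76%.
- PPV 50%: f = 0.225/0.775 = 0.290; coded risks 46.8% and 43.2%; HR 0.90; 1,310 events; power 50%.

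Fixing the PPV in the control group instead gives HR 0.84 and power 74% at PPV 75%, and 0.91 and 45% at PPV 50%.

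**6. A larger sample.** The Appendix B footnotes (35% operated, 20% lost in matching) give 10,449 × 0.35 × 0.80 × 2 ≈ 5,850 matched patients, or about 3,510 if the 60% linkage in Appendix F must also be applied (assumption; the flow diagram is not shown). At recurrence PPV 75%, the formula in step 5 gives power of about 96% and 82%. The shift in the hazard ratio stays the same.

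**The case against.** A reader might infer that the rule tests first-dislocation codes only. The text does not settle that. The quantifying sentence refers back to both kinds of coding, and its mention of first-time patients describes whose records are reviewed, not which codes are counted. This stands: the defect is an unspecified code type and no separate limit. It does not rescue the rule, because the pooled reading also passes with poor recurrence codes.

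A reader might also infer that the form cannot measure recurrence accuracy at all. It can, roughly. The primary outcome is a first event per patient, so a patient-level PPV and negative predictive value are relevant. A mixed record should be ticked No at Q6b, which makes the PPV err low. Skipping Q6c for patients with a later code matters little when that code is true, since the patient is already an event.

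Nor do the documents support saying that review visits will be counted as re-dislocations. Appendix I distinguishes new from review entries and sets out to test that distinction, and Section F says WP1 will inform the code list. Section F also has the verbal stop rule, promises sensitivity and specificity testing, and requires a report to the funder in a two-month gap before WP2. These are real safeguards, but none sets a criterion for recurrence codes, and the recurrence evidence would come largely from the same form. The Appendix H algorithm is not visible, so how confirmation enters the PPV cannot be fully judged.

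Finally, the power figures are conditional. They take the minimum sample and assume the PPV; no figure in the protocol points to 50%.

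**Conclusion.** The concern holds in a limited form. The protocol names recurrent coding as a reason to stop, but its single 75% PPV does not test it separately and can be met under either reading while recurrence codes are inaccurate. The form yields a coarse patient-level estimate from about 16 to 20 patients, assuming 80 returns and 20% to 25% with a later code.

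The size is conditional on non-differential false codes: at recurrence PPV 75% and 3,065 patients, the hazard ratio moves from 0.78 to about 0.83 and power from 90% to about 76%, with a smaller power loss in a larger matched sample. Differential miscoding, for example more coded reviews after surgery, is possible, but nothing in the protocol shows it. The point is worth correcting because it concerns a stated decision rule and a form that the protocol itself fixes.

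**What to change.** - **Section F.** State that WP2 proceeds only if the PPV reaches 75% separately for index codes and for recurrence codes, and that poor coding of either one stops the study. The 75% is the protocol's own figure; if the team prefers another limit for recurrence codes, it should state it.
- **Appendix I, Q6b.** Replace the tick with two numbers: later dislocation codes in the two years, and how many are confirmed as a new dislocation of the same shoulder.
- **Optional.** Ask Q6c of everyone. Draw half of the same 100 patients from those with a later dislocation code, and weight back when estimating the index PPV.
- **Stop-gap report.** Give the recurrence PPV with its interval.

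The cost is a change to the rule's wording and small edits to the form, with no extra questionnaires. If oversampling is used, the index PPV needs weighting and is slightly less precise. The recurrence PPV stays imprecise: with 40 returned forms from patients with a later code, 30/40 has a 95% interval of 59% to 87%, and a true PPV of 70% would still pass 31% of the time. That is why the interval should be reported alongside the pass or fail result.

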Main study (WP2): The main study (WP2) will be a population based propensity score-matched cohort study using CPRD and HES collected datasets. The cohort of participants in this study will be young adults (aged 16–35 years) with traumatic anterior shoulder dislocation (T ASD) with at least 2 years data entry in CPRD before the their first shoulder dislocation code and at 2 years follow up from their first dislocation code entry in CPRD. All events and outcomes will be collected using a pre-agreed validated list of READ CODES (CPRD) and OPCS 4.7 CODES (HES). These codes are listed in the appendices and have already been identified. They will be further validated and informed by WP1. The first read code entry in CPRD for shoulder dislocation will be defined as the ‘first dislocation’. These codes will then be routinely linked to patients and to HES.

The ***Intervention group*** will be patients in CPRD with first time T ASD who underwent shoulder stabilisation surgery after their first dislocation (early surgical repair in this NHS context will mean ‘a decision to treat surgically after the first T ASD’ and receiving surgery within 6 months). This means linking HES data to CPRD data in such a way that a HES surgical OPCS 4.7 code is seen to occur after a single first dislocation code in CPRD (without further dislocation codes) before that surgical date. The timelines between first dislocation codes and OPCS 4.7 codes will be recorded. The ***Control group***. While the most desirable control group would be physiotherapy, it is possible that WP1 will reveal that free text notes and referral codes on physiotherapy will be lacking and not reliable. If this is the case then conservative care will be defined as ‘non surgical intervention’ with no linked OPCS 4.7 surgical shoulder codes producing a control cohort of patients whose first time shoulder dislocation has been treated non-operatively. If however free text entries and referral codes for physiotherapy are reliably present in CPRD then conservative care will be physiotherapy identified by physiotherapy referral codes after a first time T ASD code. Any subsequent dislocation codes or OPCS 4.7 surgery code will be recorded.

This project was funded by the National Institute for Health Research Health Technology Assessment (project number 14/160/01).

The views and opinions expressed therein are those of the authors and do not necessarily reflect those of the HTA, NIHR, NHS or the Department of Health.

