APPENDIX D

TABLE OF CPRD DISLOCATION READ CODES

Description	READ Code	Number of clinical events currently recorded in CPRD
Dislocation or subluxation of shoulder	S41.00	51,162
Dislocation of shoulder NOS	S41z.00	11,578
H/O: dislocated shoulder	14G5.00	6,724
Closed reduction of dislocation of shoulder	7K6G300	2,878
Closed traumatic dislocation of shoulder	S410.00	2,240
Recurrent dislocation of shoulder – anterior	N083A00	2,140
Anterior dislocation of shoulder	S410111	1,864
Recurrent joint dislocation, of shoulder region	N083100	1,321
Recurrent subluxation of shoulder – anterior	N083C00	599
Closed traumatic dislocation shoulder jnt. Anterior (sub-coracoid)	S410100	439
Closed traumatic dislocation shoulder joint, unspecified	S410000	439
Closed traumatic subluxation, shoulder	S412.00	288

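### The first-dislocation rule draws on an unsplit code list containing history-of and recurrent codes, so a patient whose first code reports earlier dislocation can be indexed as first-time

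*Protocol*

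**What the plan says.** Section F (Main study, WP2) sets the index event: "The first read code entry in CPRD for shoulder dislocation will be defined as the" first dislocation. On the source of codes it says "All events and outcomes will be collected using a pre-agreed validated list of READ CODES (CPRD) and OPCS 4.7 CODES (HES"), and adds "These codes are listed in the appendices and have already been identified".

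Appendix D is the only list of dislocation Read codes. It has twelve rows in one table, with no column or note saying which codes may open follow-up and which may end it. Four rows describe something other than a new first event:

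- 14G5.00, "H/O: dislocated shoulder"
- N083A00, "Recurrent dislocation of shoulder – anterior"
- N083100, "Recurrent joint dislocation, of shoulder region"
- N083C00, "Recurrent subluxation of shoulder – anterior"

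Section I admits only patients with a first-time traumatic anterior dislocation and excludes surgery performed after more than one. Sections F and J put the surgical condition into practice by counting codes: the HES procedure must follow one dislocation code, with no further dislocation code before the surgery date. Section B says re-dislocation is identified by CPRD codes over two years.

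**The concern.** The study asks about treatment after one dislocation. If the first code on the record says that the shoulder dislocated before, or does so repeatedly, that date is not a first dislocation, yet the rule treats it as one. Three consequences follow.

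1. **Eligibility.** Patients with earlier dislocations can enter either group as first-time cases. Appendix E lists the number of dislocations before surgical repair as a risk factor for re-dislocation after surgery, so the protocol itself regards the prior count as prognostic.
2. **Outcome.** With one list for all events, a history entry made at a later visit can be read as a re-dislocation.
3. **Exposure.** A history entry between the first dislocation and surgery can be read as a further dislocation code and remove a patient who truly had surgery after a single dislocation.

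**Working it through.** **Do the rules conflict?** Take a patient aged 16-35 with more than two years of prior data whose first dislocation entry is N083A00, followed by stabilisation surgery four months later and no other dislocation code.

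- Index rule (Section F): met, because N083A00 is the first entry from the list.
- Washout (Section F): met, because there are two years of data before the entry and no earlier code. The earlier dislocation may predate the record or never have been coded.
- Surgical group rule (Sections F and J): met, because there is one dislocation code before surgery and the interval is under six months.
- Inclusion (Section I): not met in substance, because the code says the dislocation is recurrent.
- Exclusion of surgery after more than one dislocation (Section I): triggered in substance, but not by the code count.

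The operational rules admit a patient whom the eligibility criteria reject. The same holds for an unoperated patient, except that the surgical exclusion then does not apply and only the first-time criterion stands in the way.

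**How common are these codes in the list?** The inputs are the twelve event counts in Appendix D. The protocol gives no total.

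Total = 51,162 + 11,578 + 6,724 + 2,878 + 2,240 + 2,140 + 1,864 + 1,321 + 599 + 439 + 439 + 288 = 81,672.

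| Codes | Events | Share of 81,672 |
|---|---|---|
| History (14G5.00) | 6,724 | 8.2% |
| Recurrent (N083A00 + N083100 + N083C00) | 2,140 + 1,321 + 599 = 4,060 | 5.0% |
| All four | 10,784 | 13.2% |
| Remaining eight codes | 81,672 − 10,784 = 70,888 | 86.8% |

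The column counts recorded clinical events, with no age restriction. The quantity that matters is the share of patients aged 16-35 whose *first* entry is one of these codes, and the protocol does not give it.

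**Does the sample size depend on this?** No. The 656 events and 3065 patients in Section G come from the assumed rates, power and loss to follow-up.

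**The case against.** The strongest reply has three parts.

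**The list is a combined one.** The sentence defining the first dislocation does not name Appendix D, and recurrent codes have an obvious use as outcomes. A reader might infer that the protocol intends known recurrent dislocators to enter. It does not say so, and Section I points the other way. What stands is that a rule is missing: both the index definition and the list are fixed, and nothing bars these codes at index.

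**The surgical exclusion could be applied by substance.** A recurrent code before surgery shows more than one dislocation, so an analyst could exclude on it directly. That is true, but Sections F and J describe a count of codes, and the exclusion does not reach unoperated patients.

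**WP1 exists to test the coding.** Section F says the review will confirm that dislocations are first-time, that the codes will be informed by WP1, and that an updated analysis plan precedes WP2. Appendix I asks "Is there any record of a dislocation prior to the CPRD first registration date at your practice". A reader might infer that this answer is discarded because both responses lead to the next item. That is only the order of the questions; the answer is still recorded. WP1 may therefore detect the problem. However, it covers a sample, that item concerns only events before registration, and the go-ahead is a positive predictive value of at least 75% with no rule for these four codes. The Appendix H algorithm is not visible in the copy available, so how it classifies an earlier dislocation cannot be judged.

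A reader might also want S412.00 (subluxation) barred as an index code. The list does not support singling it out, because the description of S41.00, with 51,162 events, also covers subluxation.

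**Conclusion.** The point holds as a gap between the operational rules and the eligibility criteria. As written, a code that reports an earlier or recurrent dislocation can define the first dislocation, and a history code can act as an outcome or as a disqualifying further dislocation. This rests on reading the reference to the appendices as a reference to Appendix D, the only dislocation list.

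The four codes are 13.2% of listed events, and the recurrent codes alone 5.0%. A reader might infer that about 13% of the cohort is misclassified, or that at most 13% would be lost by excluding these patients. Neither follows, because event shares at all ages do not give or bound the share of patients' first codes.

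A reader might also infer a predictable shift of the hazard ratio towards 1. The protocol supplies none of the inputs for that: not the contamination in each group, not the risk in recurrent patients, not the effect of surgery in them. As an illustration with assumed figures, let 10% of each group be recurrent, with a 50% two-year risk without surgery and the planned hazard ratio, ln(0.80)/ln(0.75) = 0.776, applying to them too. Operated recurrent patients then have risk 1 − 0.5^0.776 = 0.416. The group risks become 0.9 × 0.20 + 0.1 × 0.416 = 0.222 and 0.9 × 0.25 + 0.1 × 0.50 = 0.275, and the ratio is ln(0.778)/ln(0.725) = 0.78, essentially unchanged. Unequal contamination would move it, by an amount that depends wholly on what is assumed. Size and direction therefore remain unknown.

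**What to change.** Before extraction, split Appendix D into two labelled lists and refer to them by name in Sections F, I and J.

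- **Index-eligible:** the acute dislocation and reduction codes. The four history and recurrent codes come out; this point gives no reason to change the status of the other eight.
- **History/recurrent:** 14G5.00, N083A00, N083100, N083C00. Exclude as not first-time, in both groups, any patient with one of these before the first acute code or as the first entry.
- **Same-day entries:** where 14G5.00 and an acute code fall on the same day, use a sensitivity analysis with these patients kept and then dropped.
- **Outcome:** the recurrent codes may count as re-dislocation after index. 14G5.00 is never an index code, an outcome, or a further dislocation before surgery.

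WP1 can then report how often the first entry is a history or recurrent code, which gives the patient-level figure that is now missing. The cost is a code-list edit and the loss of some index patients, in a number that the protocol does not allow one to estimate.
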